**Figure 3. Study Schematic**

## 4 OUTCOMES

### 4.1 Safety Outcomes

The following will be tracked and monitored through the course of the study

- Clinical laboratory tests (hematology, chemistry, urinalysis);
- Urine pregnancy test (UPT) for women of childbearing potential (WOCBP);
- Concomitant medications;
- Collection of adverse events (AEs);
- Vital signs;
- Injection site reactions;
- Severe hypoglycemia or hyperglycemia events monitored by CGM;
- Events of special interest:
  - Systemic or hypersensitivity reactions associated with injection, which consist of fever, chills, headache, nausea, vomiting, and/or other signs and symptoms, such as anaphylaxis, wheezing dyspnea, urticaria, and hypotension

### 4.2 Efficacy Outcomes

### 4.3 Primary Efficacy Outcomes

The primary outcome is the TOL-3021 treatment effect by a repeated measures analysis of change from baseline in the log-transformed MMTT C-peptide AUC at 12, 16, and 24 weeks of treatment.

### 4.4 Secondary Efficacy Outcomes

Secondary outcomes will include the treatment effect on:

Rate of clinically important hypoglycemia, defined as measured glucose value of <54mg/dL (3.0 mM/L) over each approximately 12-week period ending at Weeks 12, 24, 36, and 52:

- A single blood glucose level.
- By CGM,  $\geq 10$  consecutive minutes with glucose <54mg/dL.

Total daily insulin requirements in units per kilogram (kg) body weight

- HbA1c.

- Time in glycemic range 70 - 180 mg/dL

#### 4.5 Other Secondary Outcomes

The TOL-3021 treatment effect—

On a repeated measures analysis of change from baseline in the log-transformed MMTT C-peptide area under the curve (AUC) at Weeks 12, 16, 24, 52.

On number of times the CGM reports glucose levels of <70 and <55 mg/dL.

On a clinical responder analysis that will be undertaken to further characterize the treatment effect on a clinical level. A positive responder outcome will be defined as no change or an increase in C-peptide AUC from baseline between treatment and placebo at Weeks 12, 16 and 24. Upon completion of 52 week data, a similar analysis will include the 52-week data.

On non-fasting or fasting C-peptide (single test from baseline at Weeks 12, 16, 24, and 52).

On proportion of subjects in each treatment arm with HbA1c levels less than 6.5% at Week 52.

On CGM parameters:

- Time >180 mg/dL
- Time >250 mg/dL
- Mean Glucose Coefficient of Variation
- Low Blood Glucose Index (LBGI)
- Glucose below 70 mg/dL
- Area Over the Curve (AOC70)

On other measures of hypoglycemia:

- Severe hypoglycemia (SH) events (impaired or loss of consciousness requiring assistance of another).
- Documented symptomatic hypoglycemia (an event during which typical symptoms of hypoglycemia are accompanied by a measured plasma glucose concentration <70 mg/dl (3.9 mmol/L)).
- Total time <70 mg/dL by CGM.
- Nocturnal hypoglycemia, i.e., severe or documented symptomatic episodes (as defined above) occurring after the subject has retired for the primary sleeping period.

**Immunologic:**

Quantum dot responses within the qualifying subpopulation to confirm induction of specific autoantigen tolerance

Comparison of quantum dot responses within the qualifying subpopulation with clinical outcomes to confirm correlation with specific autoantigen tolerance

Determine effect of treatment on and predictive value of:

- Regulatory/protective humoral immune response to proinsulin/insulin
- Serum insulin autoantibody affinity for subjects
- Insulin autoantibody isotypes (IgA and IgM) and IgG subclasses
- Serum insulin, glutamic acid decarboxylase, IA-2, and ZnT8 antibodies by radio-binding assay (RBA) assay
- Competition assays of serum insulin and proinsulin IgM and IgG antibodies

**5 STUDY POPULATION****5.1 Number of Subjects**

Up to 99 subjects will be randomized in a 2:1 ratio of treatment with TOL-3021 to placebo with a minimum of 18 and a maximum of 24 subjects aged 12 and <18 years of age.

**5.2 Selection Criteria****5.2.1 Inclusion Criteria**

1. Diagnosis of Type 1 Diabetes Mellitus based on ADA criteria and within 5.0 years from diagnosis, defined as the first day of insulin administration.
2. Age at randomization of 12.0 – <41.0 years of age.
3. Adequate glycemic control as defined by HbA1c  $\leq 7.9\%$  based on point-of-care or local lab measurement and time in glycemic range (70-180 mg/dL)  $>55\%$  by CGM recording over 3 or more consecutive or non-consecutive days within 5 days prior to baseline mixed meal tolerance test (MMTT).
4. On insulin therapy (total insulin dose  $>0.125$  U/kg BW)
5. Presence of antibodies to at least one of the following antigens: GAD65, IA-2, ZnT8, or insulin if obtained within 10 days of the onset of exogenous insulin therapy, or documentation of positive antibodies. In the absence of a positive result for one of the specified antibodies, a diagnosis of T1D per ADA guidelines.

6. Peak C-peptide during screening 4-hour mixed meal tolerance test (MMTT)  $\geq$  0.150 nmol/L.
7. Willingness to wear the Dexcom G6 continuous glucose monitoring (CGM) device and use according to instructions including recording of total daily insulin dose taken most of each day from screening to end of treatment period.
8. Written informed consent and, for subjects aged 12-<18 years of age, patient assent and parental or guardian consent, including authorization to release health information.
9. Willingness and ability of subject to comply with all study procedures of the study protocol, including attending all clinic visits.

### **5.2.2 Exclusion Criteria**

1. Receiving a dose of acetaminophen >4,000 mg per day.
2. Body Mass Index (BMI) >32 kg/m^2 for patients 18 and older (>85th percentile for ages 12-17)
3. Previous immunotherapy for T1D within 2 years of enrollment.
4. Diagnosis of liver disease or hepatic enzymes, as defined by ALT and/or AST  $\geq$  2.5 times the upper limit of normal (ULN).
5. Hematology: white blood cells (WBC) <3 x 10^9/L; platelets <100 x 10^9/L; hemoglobin <10.0 g/dL. (Low WBC values may be repeated every 3-7 days, and results to be discussed with the Medical Monitor) Any underlying conditions likely to impact red blood cell turnover.
6. Latent autoimmune diabetes of adults (LADA), which is generally associated with preceding history and treatment of T2D with medications typically used for treatment of T2D for more than 30 days.
7. Monogenic diabetes (MODY)
8. Estimated glomerular filtration rate (eGFR) <60 ml/min, for ages 18-<41, and <75 ml/min per 1.73 m^2 for ages 12-<18.
9. History of malignancy, except for cancers in remission >5 years, or basal cell or in situ squamous cell carcinoma of the skin.
10. Significant cardiovascular disease (including inadequately controlled hypertension), history of myocardial infarction, unstable angina, use of anti-anginal medicines (e.g., nitroglycerin), or abnormal stress test, which, in the opinion of the Principal Investigator (PI), would interfere with participation in the trial.

11. Immunosuppressive therapy (systemic corticosteroids, cyclosporine, azathioprine, or biologics) within 30 days of screening.
12. Current or prior (within the last 30 days) use of metformin, sulfonylureas, glinides, thiazolidinediones, GLP1-RAs, DPP-IV inhibitors, pramlintide, or SGLT-2 inhibitors.
13. Current use of verapamil or  $\alpha$ -methyldopa.
14. History of any organ transplant, including islet cell transplant.
15. Asthma that requires oral glucocorticoid therapy. Inhaled glucocorticoid therapy is permitted.
16. Active autoimmune or immune deficiency disorder including rheumatoid arthritis, moderate-to-severe psoriasis, inflammatory bowel disease, and other autoimmune conditions that may require treatment with TNF or other biologics. Permitted autoimmune disorders include T1D or well-controlled autoimmune conditions (e.g., thyroid disease, celiac disease, and sarcoidosis, all with stable non-immunosuppressive medications for the past 30 days).
17. Thyroid-stimulating hormone (TSH) at screening  $>7.5$  mIU/L, for ages 18- $<41$  years old and  $> 3.6$  mIU/L for ages 12- $<18$  years old.
18. Adrenal insufficiency not adequately controlled on stable replacement glucocorticoid therapy.
19. Moderate non-proliferative retinopathy (NPDR) or proliferative retinopathy
20. Evidence of infection with HBV (as defined by hepatitis B surface antigen, HBsAg), HCV (anti-HCV antibodies), or HIV.
21. Subject is breastfeeding.
22. Positive urine pregnancy test at screening or at any time during the study (pregnancy tests must be performed as per the visit schedule): Females of childbearing potential must be excluded if they have a positive urine pregnancy test at screening or randomization or if they are not using medically acceptable methods of birth control. Acceptable methods of birth control include oral or transdermal contraceptives, condom, spermicidal foam, IUD, progestin implant or injection, abstinence, vaginal ring, or sterilization of partner. The reason for non-childbearing potential, such as bilateral tubal ligation, bilateral oophorectomy, hysterectomy, or 1 year or more postmenopausal must be specified in the subject's Case Report Form (CRF).
23. Males of reproductive potential who are unwilling to use medically acceptable birth control, unless the female partner is postmenopausal or surgically sterile.

24. Any social condition or medical condition that would, in the opinion of the PI, prevent complete participation in the study or would pose a significant hazard to the subject's participation.
25. Anticipated major surgery during the duration of the trial, which could interfere with participation in the trial.
26. History of drug or alcohol dependence within 12 months of screening.
27. Psychiatric disorder that would prevent subjects from giving informed consent.
28. Household members of current participants in this protocol.
29. Subjects who are not fluent in the English language.
30. Participation in other studies involving the administration of an investigational drug or experimental device, including the administration of an experimental agent for T1D within 30 days of screening, or use of an experimental therapeutic device for T1D within 30 days prior to screening. Subjects previously treated with diagnostic devices are not excluded.
31. Any current use of biotin or biotin containing supplements.

### **5.3 Discontinuation Criteria**

#### **5.3.1 Withdrawal and Early Discontinuation from the Study**

At any point after randomization, a subject may withdraw consent to be administered study medication or followed. A subject withdrawing consent to be administered study medication would be encouraged to otherwise remain in the study and to complete as many procedures as the subject is willing. The subject may withdraw entirely from study participation at any time. If the subject withdraws consent and discontinues from the study, the PI will attempt to determine the reason for discontinuation and record the reason in the subject's source documents and in the eCRF. In the event of early discontinuation from study drug, the subject will be asked to return to the site to complete the assessments specified in the End-of-Study Visit (Weeks 52 and 54).

The PI can discontinue study drug in any subject at any time if medically necessary. The PI, in consultation with the Medical Monitor, or the Medical Monitor may exercise his or her medical judgment to discontinue a subject's treatment in the study due to clinically significant changes in any clinical or laboratory parameter. Prior to discontinuing a subject from study participation, the PI will discuss his or her intentions with the Medical Monitor.

The discontinuation eCRFs (End of Medication and Study Termination) must be completed for every subject who received study medication regardless of the subject's study

completion status. The primary reason for any early discontinuation should be indicated on these eCRFs. Standard categories of early termination include:

- *Adverse event*: Reasons for discontinuation may include serious and non-serious AEs regardless of relation to study medication, or decision on the part of the subject to discontinue due to an AE.
- *Investigator judgement*: Clinical observations or laboratory results led the PI, in his or her medical judgement, to conclude that discontinuation was in the best interest of the subject. The reason should be specified in the eCRF.
- *Death*: The subject died.
- *Withdrawal of consent*: The subject decided to withdraw from further participation in the study in the absence of a medical need as determined by the PI. The reason for discontinuation should be recorded on the eCRF.
- *Protocol deviation*: The subject's findings or conduct failed to meet the protocol entry criteria post-randomization or subject failed to adhere to the protocol requirements. The deviation necessitated premature termination from the study.
- *Lost to follow-up*: The subject failed to attend visits and study personnel were unable to contact the subject after two attempted phone calls and a registered letter.
- *Other*: The subject was terminated for a reason other than those listed above. The reason should be specified in eCRF.

The Sponsor reserves the right to terminate the study at any time, especially if the scientific question is no longer relevant or if the study objectives will not be met. All data normally collected at completion of the study must be collected either at the time of the subject's early termination or on or before the scheduled study closeout visit. Reasons for termination of the study include:

- AEs occur with such severity and frequency that adherence to the proposed schedule cannot be continued;
- Risks that cannot be adequately quantified;
- Failure to remedy deficiencies identified through site monitoring, failure to meet identified Sponsor performance standards, or substandard data;
- Sponsor decision to discontinue the development of the product or the indication under study.

### **5.3.2 Trial Stopping Rules**

Study enrollment or study drug administration may be suspended if certain events occur during the trial. The chairman of the DSMB will be notified that a review of safety data

may be required to determine procedures that need to be implemented if any of the following occur:

- Any death deemed to be related to study therapy
- More than one hospital admission of the same event based on MedDRA preferred term for an unexpected treatment-related SAE
- Three of the first 10 subjects, or 30% thereafter, require discontinuation of study medication for the same or similar serious adverse event based on MedDRA preferred term or at the discretion of Sponsor and/or Medical Monitor

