## **7 UNBLINDING**

The PI and site staff are blinded to subject treatment throughout the study and do not have access to the randomization code. Unblinding assignments will be maintained by the unblinded statistician at Emmes that prepared the randomization code.

[figure not shown]
In case of an unexpected and related SAE for which knowledge of the subject's treatment is required for the subject's clinical care and safety, the blind for that subject may be broken. The PI must contact the Medical Monitor with an explanation of the need to obtain the study treatment information. The Medical Monitor will confer with the Sponsor prior to the authorization of the blind to be broken. Complete documentation of breaking the blind must be recorded in the subject's source documents including the date and time the blind was broken, the reason for the decision to unblind, and the names of the personnel involved in the decision. The unblinded statistician will conduct the unblinding, notify the site PI, and also the DSMB of all such cases.

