## 11 ADVERSE EVENTS

### 11.1 Definitions

An **Adverse Event (AE)** (also referred to as an adverse experience) is any untoward medical occurrence (e.g., sign, symptom, disease, syndrome, intercurrent illness, clinically significant abnormal laboratory finding, injury, or accident) that emerges or worsens following administration of the study drug and until the end of study participation. The untoward medical occurrence may not necessarily have a causal relationship to the administration of the investigational product. An AE can therefore be any unfavorable and/or unintended sign (including a clinically significant abnormal laboratory result), symptom, or disease temporally associated with the use of a medicinal (investigational) product, whether or not related to the medicinal (investigational) product.

A **Suspected Adverse Reaction (SAR)** is any adverse event for which there is a reasonable possibility that the study drug caused the event. A reasonable possibility implies that there is evidence to suggest a causal relationship between the drug and the AE. Suspected adverse reaction implies a lesser degree of certainty about causality than adverse reaction.

An **Adverse Reaction (AR)** is any adverse event caused by the study drug.

**Serious Events, including SAE, Serious Suspected Adverse Reaction (SUSAR), or Serious Adverse Reaction (SAR)**, as determined by the PI or the Sponsor, are any event that results in any of the following outcomes:

- Death
- Life-threatening condition (i.e., the subject was, in the opinion of the PI, at immediate risk of death from the event as it occurred. It does not apply to an AE that hypothetically might have caused death if it were more severe)
- Persistent or significant disability/incapacity (i.e., the AE results in a substantial disruption of the subject's ability to carry out normal life functions)
- (Note: The term disability means a substantial disruption of a person's ability to conduct normal life functions. This definition is not intended to include experiences of relatively minor medical significance, such as uncomplicated headache, nausea, vomiting, diarrhea, influenza-like illness, or accidental trauma (e.g., sprained ankle),

which may interfere or prevent everyday life functions but do not constitute a substantial disruption.)

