- In-patient hospitalization or prolongation of existing hospitalization (i.e., the AE required at least a 24-hour in-patient hospitalization or prolonged a hospitalization beyond the expected length of stay. Hospitalizations for elective medical/surgical procedures, scheduled treatments, or routine checkups are not SAEs by this criterion)
- Congenital anomaly/birth defect (i.e., an adverse outcome in a child or fetus of a subject exposed to the molecule or investigational product before conception or during pregnancy)
- Important medical event – does not meet any of the above serious criteria but may jeopardize the subject or may require medical or surgical intervention to prevent one of the outcomes listed above. Examples of such medical events include allergic bronchospasm requiring intensive treatment in an emergency room or at home, blood dyscrasias or convulsions that do not result in inpatient hospitalization, or the development of drug dependency or drug abuse

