### **11.8.3.3 Collection and Follow-up of AEs and SAEs**

Qualified research staff will elicit subject reporting of AEs, including SAEs, from the time the subject signs informed consent. The research staff will obtain as much information as possible about the reportable AE/SAE to complete the AE/SAE CRF(s) and will consult with the PI as warranted. The information will be reviewed by the PI and assessed for seriousness, severity, and causal relationship. Appropriate site staff will review all AE documentation and verify accuracy of assessments to ensure that all AEs are appropriately reported and to identify any unreported AEs that require reporting. Each participating site's

PI is responsible for study oversight, including ensuring human research subject protection by designating appropriately qualified, trained research staff and assessing, reporting, and monitoring AEs.

CRA's will visit the study sites and review the study data on a regular basis. They will also promptly advise sites to report any previously unreported AEs and ensure that the AEs are being followed appropriately by the research staff. The CRA will ensure that any unreported or unidentified SAEs discovered during visits are promptly reported by the site. Staff education, re-training, or appropriate corrective action plan will be implemented at the participating site when unreported or unidentified AEs are discovered, to ensure future identification and timely reporting by the site. The study Medical Monitor or his/her designee will review all reported AEs/SAEs throughout the study. Multiple safety monitoring layers will be provided by:

- All SAEs reported will undergo Medical Monitor review within one business day of notification of the SAE
- Weekly review of all reported AEs using listings generated from the data system; the review will entail both what was reported in the preceding week and cumulatively from study inception for trends and safety signals
- MedDRA coding of all AEs will be performed on a quarterly basis to ensure consistency of terminology; the coding process will also entail review for trends and safety signals
- Document preparation for periodic DSMB meetings; cumulative safety data will be reviewed for trends and safety signals at the time of document preparation and review

The study DSMB will also review safety data for this trial periodically at regularly scheduled meetings.

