#### **13.3.2 Safety Analysis**

All randomized subjects who received treatment will be included in a final safety data analysis which will include all data through Week 52 as the as-treated cohorts. In addition to descriptive summaries of all AEs by treatment group, Fisher's Exact test will be used to compare the incidence of the most frequent AEs or SAEs between treatment groups. The MedDRA system will be used to map each AE verbatim term to the system organ class (SOC) and preferred term (PT) for summary purposes. AE data, including the AE verbatim term and the associated AE preferred term, will be provided in the subject data listings. Note that once enrollment of TOL-3021 studies is expanded to adolescent participants aged 12.0 to <18 years of age, data from adolescent participants will be summarized and presented separately from data on adult participants in all subsequent DSMB review meetings.

Adverse event incidence summaries, including incidence rates of SAEs and TEAEs, will be generated on a monthly basis on live data. These will be reviewed in real time by the Sponsor and Emmes, with the treatment groups labeled as "A" and "B." An excessive rate in any specific AE or SAE may result in referral to the DSMB for review. The study statistician will maintain these reports and all resulting correspondence. The code may be requested to be broken by the DSMB after receiving Sponsor approval.

Other safety data, such as laboratory data, physical examination data, and abnormal findings, will be tabulated and/or graphically displayed. Concomitant medications used during the study will be summarized. Medications discontinued prior to the randomization date will be excluded from the summary.

Safety data collected after Week 52 will be analyzed separately from safety data collected during the controlled trial period.

After 6 subjects aged 14-<18 years of age have been enrolled with the last subject having a minimum of 2 injections with at least 1 week follow-up after the 2nd injection. Safety data from these initial subjects will be evaluated before opening the study to subjects 12 and older.

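### The low-count safety trigger in section 5.3.2 counts hospital admissions, so repeated unexpected, related SAEs without admission bring no defined notice to the DSMB chair

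*Protocol*

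**What the plan says.** Section 5.3.2 gives three circumstances in which the DSMB chair is to be told that a safety review may be needed:

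1. a death judged related to study therapy;
2. "More than one hospital admission of the same event based on MedDRA preferred term for an unexpected treatment-related SAE";
3. discontinuation of study drug for the same or similar SAE in 3 of the first 10 subjects, or 30% thereafter, "or at the discretion of Sponsor and/or Medical Monitor".

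Section 11.1 defines seriousness by six alternative criteria. Hospitalisation is one of them, met when "the AE required at least a 24-hour in-patient hospitalization" or when an existing stay is prolonged. A subject who was "at immediate risk of death from the event as it occurred" also has a serious event, with no reference to admission. So does a subject with an important medical event, for which the protocol's examples include "blood dyscrasias or convulsions that do not result in inpatient hospitalization" and bronchospasm treated intensively in an emergency room or at home.

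Outside 5.3.2, the protocol describes several further reviews:

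- Section 11.8.3.3: "All SAEs reported will undergo Medical Monitor review within one business day of notification of the SAE", plus a weekly cumulative review of all AEs.
- Section 13.3.2, on the monthly summaries by masked group: "An excessive rate in any specific AE or SAE may result in referral to the DSMB for review".
- Section 7: if a subject's blind is broken, the unblinded statistician is to "notify the site PI, and also the DSMB of all such cases".
- Section 11.8.3.1: cumulative AE reports go to the DSMB as its charter provides.
- Section 11.8.3.2: all SAEs go to the DSMB quarterly.

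**The concern.** The second trigger is the rule meant to catch a small cluster of the same unexpected drug reaction. Its counting unit is the admission, so place of care decides whether the chair is told. Two subjects kept in hospital for a day with a related, unexpected event bring notice. Two subjects with a life-threatening or medically important event of the same term, treated and sent home, do not.

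This bears on the product under study. Section 4.1 names injection-associated hypersensitivity, including anaphylaxis, wheezing and hypotension, as events of special interest. Most injections are self-administered at home, and enrolment is being opened to ages 12 to under 18. Such reactions can be managed without admission, although any already listed in the Investigator's Brochure would be expected and so outside this trigger in any case.

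What is at stake is how surely and how soon an independent body hears of a second event. Individual care is not at stake: under section 5.3.1 the investigator or the Medical Monitor can stop drug in any subject.

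**Working it through.** The protocol states no operating characteristic for these rules, so there is no figure to reproduce. The check sets the texts side by side and then sizes the gap.

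**Step 1. What each trigger does with repeated, unexpected, related, non-fatal SAEs of one term when nobody is admitted**

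| Trigger in 5.3.2 | Outcome |
|---|---|
| Related death | Not met |
| More than one admission | Count is 0, however many events occur |
| Drug stopped, numeric part | Needs 3 of the first 10, then 30% |
| Discretion clause | Possible, not required |

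**Step 2. Size of the 30% threshold.** Taking the denominator as cumulative (5.3.2 does not define it): 0.30 × 30 = 9; 0.30 × 90 = 27; 0.30 × 99 = 29.7, so 30. Each of these subjects must also stop drug. The contrast is 2 events if admitted, against 3 of the first 10, then 9 of 30, 27 of 90 or 30 of 99 discontinuations if not. Even the early threshold is hard to reach: at a 5% event rate, P(at least 3 of 10) = 0.012.

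**Step 3. The other routes to the DSMB**

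- Discretionary: the clause in 5.3.2, informed by Medical Monitor review; referral after the monthly review (13.3.2).
- Conditional: notice once a blind is broken (section 7).
- Set elsewhere: reports under the DSMB charter (11.8.3.1).
- Dated: the quarterly SAE report (11.8.3.2). The interval is 52/4 = 13 weeks, so the wait from the second event is 0 to 13 weeks, with mean 13/2 = 6.5 weeks if events fall evenly over the quarter. This applies only if no other route acts first.

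**Step 4. Illustration of how often the gap could arise.** Section 13.1 gives up to 99 subjects randomised 2:1, so 99 × 2/3 = 66 on active drug. Let X ~ Binomial(66, p) be the number with one unexpected, related SAE term, and let s be the share admitted. Admitted subjects are then Binomial(66, p·s). Two admissions imply two events, so

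P(at least 2 events, fewer than 2 admitted) = P(X ≥ 2) − P(admitted ≥ 2).

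The rates p and shares s are assumptions; no document gives them.

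| p | P(X ≥ 2) | P(admitted ≥ 2), s = 25 / 50 / 75% | Gap, s = 25 / 50 / 75% |
|---|---|---|---|
| 1% | 0.141 | 0.012 / 0.043 / 0.088 | 0.129 / 0.098 / 0.053 |
| 2% | 0.381 | 0.043 / 0.141 / 0.261 | 0.338 / 0.240 / 0.121 |
| 3% | 0.593 | 0.088 / 0.261 / 0.439 | 0.505 / 0.332 / 0.154 |
| 5% | 0.848 | 0.200 / 0.494 / 0.713 | 0.649 / 0.355 / 0.135 |

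**Step 5. Which rates are plausible.** In the predecessor study (section 1.1) 14 + 18 + 14 + 8 = 54 subjects were randomised to active drug, and every SAE was judged unrelated. With 0 of 54, the one-sided 95% upper bound is 1 − 0.05^(1/54) = 0.054 for any related SAE over 12 weeks at mixed doses. A single unexpected term is a narrower class, which favours the lower rows. Dosing here lasts 52 weeks, which works in the other direction.

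**The case against.** The strongest reply is that nothing here is an error. The sections do not contradict each other, and a low-count trigger need not cover every ground for seriousness. Admission is a fairly objective severity filter, whereas an important medical event rests on judgement. Oversight is also layered. The Medical Monitor reviews each SAE within a business day and all AEs weekly and cumulatively. The DSMB chair may convene an extra meeting (section 5.4). Section 11.8.3.2 requires expedited reports from the first serious, unexpected, related event, within 7 days to FDA if fatal or life-threatening and within 15 days to FDA and all investigators otherwise. The charter and the Safety Monitoring Plan (section 11.9) may already oblige prompt notice. A met trigger stops nothing in any case. Finally, the probabilities rest on assumed inputs: at a 0.5% rate the gap is only 0.02 to 0.04 over the same admission shares, and if 90% of events are admitted it is at most 0.06 at every rate in the table.

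Much of this stands. It limits the weight of the point and makes the 13 weeks a worst case. It does not close the gap. None of the routes visible in the protocol obliges anyone to tell the chair promptly of a second event: expedited reports are addressed to FDA and investigators, and the chair cannot convene over events not yet reported. The filter also fails on its own terms, because a life-threatening event treated without admission is no milder than a one-day stay. Section 5.3.2 states its trigger without deferring to the charter.

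**Conclusion.** The point holds as a weakness in a stated rule, worth correcting but not critical. As written, repeated unexpected, related SAEs of the same preferred term count as zero under the second trigger when no subject is admitted, and the other numeric triggers do not substitute. Defined notice needs 2 events with admission; without it, 3 of the first 10 subjects or 30% thereafter must stop drug.

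If every discretionary, conditional and charter route fails, the wait is at most 13 weeks. For half of events admitted, the chance that the gap arises is about 0.10 at a 1% rate and 0.24 at 2%; across admission shares of 75% to 25% the ranges are 0.05 to 0.13 and 0.12 to 0.34. These figures assume 66 active subjects and independent events, and they illustrate the size of the gap without estimating any delay. Confidence is medium, because the charter and the Safety Monitoring Plan are not available and could already provide the notice.

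**What to change.** In the second bullet of section 5.3.2, replace the count of hospital admissions with more than one occurrence of the same event by preferred term, counted over SAEs that meet any criterion in section 11.1. Keep the restriction to unexpected, treatment-related SAEs, so that background and expected events do not trigger it. Leave suspension discretionary, and check that the DSMB charter and the Safety Monitoring Plan use the same wording.

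The change is one phrase. Under section 15.6 it needs a written amendment with IRB approval and regulatory submission, so it is best bundled with the next amendment. It needs no new data, because section 11.8.3.2 already requires these events to be classified as serious, unexpected and related for expedited reporting. The likely cost in running the trial is a few more notices to the chair.
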